11.7.3 Medically Attended Adverse Events

All AEs where subjects are seeking medical care (i.e. doctor's office, emergency service, hospital, but not including use of self-medication). This will be identified by the Investigator and recorded on the CRF.

11.7.4 Serious Adverse Events

An SAE is defined as any untoward medical occurrence that at any dose meets one or more of the following criteria:

- Outcome is fatal/results in death (including fetal death);
- Is life-threatening – defined as an event in which the subject was, in the judgment of the Investigator, at risk of death at the time of the event; it does not refer to an event that hypothetically might have caused death had it been more severe;
- Requires inpatient hospitalization or results in prolongation of an existing hospitalization;
- Results in persistent or significant disability/incapacity (i.e., a substantial disruption of a person's ability to conduct normal life functions);
- Results in congenital anomaly/birth defect;
- Is a medically important condition – a medical event that may not be immediately life-threatening or result in death or require hospitalization but may jeopardize the subject or may require medical or surgical intervention to prevent one of the other outcomes listed in the definitions above. This definition also applies to progression of disease leading to a serious outcome.

All criteria leading to an AE being classified as an SAE will be recorded on the eCRF. AEs graded as potentially life-threatening (Grade 4) as per FDA Guidance on Toxicity Grading Scales will be reported as SAEs and reported as Severe (Grade 3).

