17.2.2 Solicited Adverse Events

17.2.2.1 Injection Site Reaction – Measurement and Evaluation

Subjects will be provided with a measuring device to measure the size of any measurable injection site reaction that may develop after vaccination. The subject will be instructed on how to measure any such reactions over a period of 10 consecutive days starting on the day of vaccination along the longest diameter of the reaction area and record this measurement in the Subject eDiary. Injection site reactions include injection site pain, tenderness, erythema/redness, induration and swelling.

Injection site reactions will be rated based on the FDA Guidance on Toxicity Grading Scales as described in Table 17.2-1. Any grade 4 injection site reaction should be reported as an SAE (see Section 17.1.2).

Table 17.2-1
Grading of Injection Site Reactions – Vaccine Specific Criteria

Vaccine-specific Criteria	Mild (Grade 1)	Moderate (Grade 2)	Severe (Grade 3)	Potentially Life Threatening (Grade 4) ^c
Pain	Does not interfere with activity	Repeated use of non-narcotic pain reliever > 24 hours or interferes with activity	Any use of narcotic pain reliever or prevents daily activity	Emergency room (ER) visit or hospitalization
Tenderness	Mild discomfort to touch	Discomfort with movement	Significant discomfort at rest	ER visit or hospitalization
Erythema / Redness ^a	2.5 – 5.0 cm 0.98 – 1.96 inch	5.1 – 10.0 cm 1.97 – 3.94 inch	> 10.0 cm > 3.94 inch	Necrosis or exfoliative dermatitis
Induration / Swelling ^b	2.5 – 5.0 cm (0.98–1.96 inch) and does not interfere with activity	5.1– 10.0 cm (1.97 – 3.94 inch) or interferes with activity	> 10.0 cm (> 3.94 inch) or prevents daily activity	Necrosis

^a In addition to grading the measured local reactions at the greatest single diameter.

^b Induration / swelling should be evaluated and graded using the functional scale as well as the actual measurement.

^c Any Grade 4 injection site reaction will be reported as SAE, Grade 3 severity should be documented.

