18.4.2 Secondary Endpoints

18.4.2.1 Secondary Safety Endpoints

Safety tabulations will generally be provided separately for solicited AEs and unsolicited AEs, and for both types of AEs combined. 95% confidence intervals according to Altman will generally be provided for all AE rates and differences between the three Lots will be

assessed for significance using Fisher's exact test. Further details in addition to the outline below will be provided in the SAP.

The number and percentage of subjects with any AE, any solicited AE, unsolicited AE, any related unsolicited AE, any related severe AE, any SAEs, any related SAEs, any AESI, any related AESI, any medically attended AE, any AE leading to withdrawal from study, and any AE occurring at a frequency of at least 10% and at least 1% in at least one treatment group, up to Day 29, and up to Month 6, will be presented for each Lot overall and by system organ class/preferred term. Differences between the Lots will be assessed for significance using Fisher's exact test, a significant overall test will be amended by pair-wise tests.

Changes in laboratory values from study entry will be analyzed descriptively and will be part of the unsolicited AE evaluation only in case of clinically relevant deviations. The rates of subjects with laboratory assessments outside the normal range, and with abnormal laboratory parameters falling into the grade 0 vs. 1 through 3 will be calculated by visit and overall. The rate of subjects with urinalysis results according to the test manufacturer's results categories will be calculated.

All subjects entered into the study, who receive the single vaccination, will be included in the safety analysis.

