Fibrinogen decrease - mg/dL	150 – 200 ⁴	125 – 149	100 – 124	< 100 or associated with gross bleeding or disseminated intravascular coagulation (DIC)

¹ In case the laboratory's normal ranges and absolute Grade 1 limits overlap, Grade 1 limits will prevail, i.e. the value will be classified as Grade 1 abnormality even if it is within central laboratory normal ranges. Values between the central laboratory normal ranges and absolute Grade 1 limits will be reported as no abnormality (Grade 0).

² The clinical signs or symptoms associated with laboratory abnormalities might result in characterization of the laboratory abnormalities as Potentially Life Threatening (Grade 4). For example, a low sodium value that falls within a grade 3 parameter (125-129 mEq/L) should be recorded as a grade 4 hyponatremia unsolicited AE if the subject had a new seizure associated with the low sodium value.

³ As neither the FDA Scale nor the Division of AIDS Table for Grading the Severity of Adult and Pediatric Adverse Events (December 2004) provide any grading for Hematocrit, Erythrocyte count, Monocytes, Basophils, ESR and CRP, these will only be analyzed as "outside normal range", as determined by central laboratory standards and graded as described in Section 17.2.1.1 upon investigator's judgement

⁴ Central laboratory values should be adjusted to FDA toxicity grading scale. Specifically, if central laboratory reference range is more stringent than FDA toxicity grading scale the central laboratory values should be reported as no abnormality (Grade 0). Similarly, if laboratory values are within the central laboratory normal reference range, but fall into FDA toxicity grading scale, the values should be reported as indicated by the FDA toxicity grading scale.

⁵ "ULN" is the upper limit of the normal range.

[figure not shown]
⁶ Any grade 4 abnormal laboratory value should be reported as an SAE (see Section 17.1.2).

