11.7.1 Adverse Events Severity

All AEs will be assessed for severity by the Investigator using his/her clinical expertise. Severity will be categorized as Mild (Grade 1), Moderate (Grade 2) or Severe (Grade 3).

If the severity rating for an ongoing AE changes before the event resolves, the AE will not be reported a second time. Instead the original AE report will be revised. For purposes of data capture the highest severity rating during the course of a single AE will be the severity rating entered on the AE CRF. Any AE with missing severity will be classed as severe.

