11.7.6.1 Injection Site Adverse Events

Solicited injection site AEs include injection site pain, tenderness, erythema/redness and induration/swelling. The severity for these AEs will be rated based on the FDA Guidance on Toxicity Grading Scales as described in Table 17.2-1 of the Protocol. Any grade 4 injection site AE should be reported as an SAE and will be reported as Severe (Grade 3) (see Section 11.7.4).

¹ The update regarding the anatomical location of cutaneous pruritus is included to provide further clarification. This information is not included in the current Protocol Version 3.0. However, this definition will be included in all subsequent CSPs.

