11.7.6.2 Systemic Adverse Events

Systemic AEs include fever, nausea/vomiting, headache, fatigue, myalgia (muscle pain), arthralgia (joint pain) and rash will be reported in a standardized manner over a period of 10 consecutive days after vaccination.

Severity for systemic AEs will be rated based on the FDA Guidance on Toxicity Grading Scales as described in Table 17.2-2 of the Protocol. Any grade 4 systemic AE should be reported as an SAE and will be reported as Severe (Grade 3) (see Section 11.7.4).

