13.5.1 Adverse Events

Safety tabulations will generally be provided separately for solicited AEs and unsolicited AEs, and for both types of AEs combined. Number and proportion of subjects, plus number of events in each category will generally be presented. 95% confidence intervals will be provided for all AEs, SOC and PT. Differences between the three Lots will be assessed for significance using Fisher's exact test.

Summaries of AEs categorized by SOC and PT coded according to the MedDRA dictionary will be produced. Within these summaries counting will be by subject not event and subjects are only counted once within each SOC or PT.

Where AEs are presented by severity (Mild, Moderate, Severe), SOC and PT, subjects with multiple events within a particular body system or preferred term will be counted once under the category of their most severe event within that SOC or PT.

In summaries of AEs which are categorized by relationship to IMP, SOC and PT, AEs with a causality reported as probable or possible will be considered related to the IMP. Subjects with multiple events within a particular SOC or PT will be counted under the category of their most drug-related event within that SOC or PT.

All AE tabulations will be presented for the Safety analysis set.

All AEs recorded on the CRF will be listed.

Furthermore, the following tabulations of AEs will be produced:

- All unsolicited AEs up to study Day 29 will be presented by SOC and PT, as well as summaries by SOC, PT and severity. Treatment groups will be compared using Fisher's exact test (Part A);
- Solicited injection site and systemic AEs within 10 days post-vaccination by PT (Part A);
- Solicited injection site and systemic AEs within 10 days post-vaccination by PT and severity (Part A);
- All AEs during the entire study period by SOC and PT (Parts A, B);
- All AEs during the entire study period by SOC, PT and severity (Parts A, B);
- All Related AEs during the entire study period by SOC and PT (Parts A, B);
- SAEs by SOC and PT during entire reporting period (Parts A, B);
- Related SAEs by SOC and PT during entire reporting period (Parts A, B);
- AESI within 2 to 21 days post-vaccination by SOC and PT (Part A, B);
- AESI for ongoing events from Part A (Part B);
- Related AESI within 2 to 21 days post-vaccination by SOC and PT (Part A, B);

In addition, the following tables will also be presented for the specified study part:

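### Grade 4 has no category in the planned laboratory grade rates, and for solicited reactions it is merged into Grade 3, so no severity table can show it separately

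*SAP*

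**What the plan says.** **Scales.** Protocol Tables 17.2-1 and 17.2-2 grade solicited injection site and systemic reactions up to Grade 4 (rash stops at Grade 3). Protocol 24.3 grades most laboratory parameters up to Grade 4 and adds: "Any grade 4 abnormal laboratory value should be reported as an SAE".

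**Laboratory analysis.** Protocol 18.4.2.1 plans rates of subjects outside the normal range, and rates with "abnormal laboratory parameters falling into the grade 0 vs. 1 through 3 will be calculated by visit and overall". SAP 13.5.2 says which samples are assessed and when, but names no table by toxicity grade.

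**Solicited reactions.** The footnote to protocol Table 17.2-1 reads "Any Grade 4 injection site reaction will be reported as SAE, Grade 3 severity should be documented", and Table 17.2-2 carries the same instruction for systemic reactions. The SAP carries this forward for injection site AEs in 11.7.6.1 ("Any grade 4 injection site AE should be reported as an SAE and will be reported as Severe (Grade 3")) and for systemic AEs in 11.7.6.2 ("Any grade 4 systemic AE should be reported as an SAE and will be reported as Severe (Grade 3")). SAP 11.7.4 states the general rule, that Grade 4 AEs "as per FDA Guidance on Toxicity Grading Scales will be reported as SAEs and reported as Severe (Grade 3").

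**AE severity levels.** SAP 11.7.1: "Severity will be categorized as Mild (Grade 1), Moderate (Grade 2) or Severe (Grade 3"). Protocol 17.2.1.1 has the same three levels. SAP 13.5.1 builds its severity tables on them: "Where AEs are presented by severity (Mild, Moderate, Severe), SOC and PT".

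**The concern.** Frequency and severity of solicited reactions, of unsolicited AEs and of all AEs are secondary safety endpoints (protocol 12.3.2, SAP 9.3). The plan defines a top severity category and then provides no severity table in which it can be seen. For laboratory values the rule as written has no place for the worst results: a neutrophil count below 500 cells/mm³ is Grade 4 in protocol 24.3 and is neither Grade 0 nor Grades 1 to 3. For solicited reactions, a fever above 40.0 °C sits in the same row as one of 39.0 °C.

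The study is meant to enlarge the safety database for the final dose (protocol 10.4). A reader of that database would want to know whether any severe reactions reached Grade 4.

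**Working it through.** The plan gives no figure to reproduce, so the check sets the passages side by side and adds one line of arithmetic.

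| Data | Grades defined | Grades in the planned severity analysis | What happens to Grade 4 |
|---|---|---|---|
| Solicited injection site (Table 17.2-1) | 1 to 4 | Mild, Moderate, Severe | Documented as Grade 3, flagged as SAE |
| Solicited systemic (Table 17.2-2) | 1 to 4; rash 1 to 3 | Mild, Moderate, Severe | Same |
| Laboratory values (protocol 24.3) | 0 to 4 for most parameters | 0, and 1 to 3 (protocol 18.4.2.1) | No named category |
| Unsolicited AEs (protocol 17.2.1.1, SAP 11.7.1) | 1 to 3 | Mild, Moderate, Severe | See step 4 |

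1. **Does the SAP repair the laboratory gap?** No. SAP 13.5.2 has no grade table, and SAP 6.1, which lists changes from the protocol, does not mention laboratory grading.

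2. **Where does the merging of solicited Grade 4 begin?** In the protocol. The footnotes to the two grading tables ask for Grade 3 to be documented, so the severity field on the AE page may never hold a 4.

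3. **Can Grade 4 be seen elsewhere?** Partly. SAP 13.5.1 plans SAE tables by SOC and PT, summary rows for related solicited and related unsolicited SAEs, a maximum fever temperature table up to Day 11, and listings of all AEs. The SAE tables and rows carry no grade, so a Grade 4 reaction there looks like an SAE that qualified on another criterion. The temperature table helps for fever only. The outside-normal-range rate includes abnormal laboratory values of any grade without separating them. The Severe row also takes in AEs whose severity is missing (SAP 11.7.1), so it mixes Grade 3, Grade 4 and unknown.

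4. **Do the passages agree on a Grade 4 laboratory AE?** No. Protocol 17.7.5 has clinically relevant laboratory abnormalities assessed for severity on the 24.3 scale. Footnote 2 to that scale gives a low-sodium case to be recorded as a Grade 4 unsolicited AE. Protocol 17.2.1.1 and SAP 11.7.1 offer only three levels, and SAP 11.7.4 reports such an event as Grade 3.

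5. **Size per event.** Inputs: 134 subjects per lot (protocol Table 3); 10% assumed drop-out (protocol 18.1). One subject left out of the numerator changes a lot's rate by 1/134 = 0.0075, or 0.75 percentage points. At a late visit with 10% drop-out, 134 × 0.90 ≈ 121 remain, and 1/121 = 0.83 percentage points. For the overall rate the effect is nil if the same subject also has a Grade 1 to 3 value on that parameter at another visit and is counted on it.

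**The case against.** The strongest reply is that three levels plus an SAE flag is a consistent, prespecified convention. The protocol orders it at data capture and the SAP follows. Every Grade 4 AE counts as Severe and as an SAE, its SAE criteria are recorded on the eCRF (SAP 11.7.4), and the DSMB reviews SAE cases ad hoc (protocol 17.11.1). This stands as far as it goes. Seriousness is a different attribute from severity, however, and an ungraded SAE table does not restore the missing level.

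Four stronger readings are tempting, and the documents do not support them.

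- A reader might infer that life-threatening reactions vanish or are wrongly reported. They do not: what is lost is the split within Severe, and Grade 4 fever is visible in the temperature table.
- A reader might infer that the SAP departs from the protocol on solicited reactions. It does not: the protocol footnotes come first.
- A reader might infer that Grade 4 laboratory subjects are certain to drop out of the graded rates. The text leaves them without a category. A programmer could apply SAP 11.7.4 by analogy and put them in Grade 3, but that section concerns AEs, not laboratory values. The wording is open, which is reason enough to settle it.
- A reader might scale up the 13.3% of Phase 1 medium-dose subjects with neutropenia, leukopenia and/or lymphocytopenia (protocol 10.5.3) to this trial. That figure carries no grade and says nothing about Grade 4.

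It is also fair to object that a Grade 4 is not shown to be stored for every reaction. Subjects enter only absence, presence and duration in the eDiary (footnote to protocol 17.3), and the analysed solicited AEs are those on the AE page (SAP 11.7.6).

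**Conclusion.** The point holds as a reporting gap. Protocol 18.4.2.1 is incomplete as written, because its graded laboratory rates omit a grade that protocol 24.3 defines. For solicited reactions, both documents merge Grade 4 into Grade 3, and no planned severity table separates them. The low-sodium example in the 24.3 footnotes contradicts the three-level AE scale and SAP 11.7.4, and these passages must be reconciled.

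The size cannot be stated as an expected count, since the documents give no Grade 4 rate and the number may be small. Per omitted laboratory subject it is about 0.75 percentage points of a lot's rate, assuming all 134 subjects are in the denominator. The primary analysis, sample size and power are untouched.

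The conclusion rests on the legible text. SAP Table 9-1 is blacked out and table shells are not public, so a grade table could exist there. The SAP's safety sections do not refer to one.

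**What to change.** 1. In protocol 18.4.2.1, extend the graded laboratory rates to Grades 0 through 4, reported by grade, and state whether the overall rate uses each subject's worst grade. Add the same table to SAP 13.5.2.
2. In the SAP, keep toxicity grade as an analysis variable separate from the three-level AE severity. Where the AE page holds only three grades, derive it from recorded temperature, central laboratory values, and the SAE criteria or SAE forms.
3. In the solicited severity tables, show Grade 4 as its own row wherever the scale defines it (not for rash), with a Grade 3-or-higher total. That total keeps every existing severe row unchanged. Revise SAP 11.7.4, 11.7.6.1 and 11.7.6.2 to match.
4. Align the footnotes to protocol Tables 17.2-1 and 17.2-2 with this. Changing only the SAP would create a new conflict between the documents.
5. Reconcile footnote 2 of protocol 24.3 with protocol 17.2.1.1 and SAP 11.7.1 and 11.7.4.

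The cost is wording, some derivation and table shells. The main limit is that Grade 4 may not be recoverable for some symptom-based reactions, such as pain, headache or myalgia. Where it is not, the table should say so and leave the event in the Grade 3-or-higher total.

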11.7.5 Adverse Events of Special Interest

An AESI is an event of scientific and medical concern specific to the Sponsor's product. In addition to nonspecific transient muscle pain and joint pain which may occur after any vaccination, the AESI for VLA1553 include signs and symptoms suggesting an acute stage CHIKV-associated event.

The following cluster of symptoms suggestive of CHIKV infection with or without remissions or exacerbations will receive particular consideration:

1. Fever ($\geq 38.0^{\circ}\text{C} / 100.4^{\circ}\text{F}$ measured orally);

AND

2. Acute (poly)arthralgia/arthritis most frequently in the extremities (wrists, ankles and phalanges, often symmetric), back pain and/or neurological symptoms (e.g. confusion, optic neuritis, meningoencephalitis or polyneuropathy) and/or cardiac symptoms (e.g. myocarditis);

OR

One or more of the following signs and symptoms: macular to maculopapular rash (sometimes with cutaneous pruritus (foot plant¹) and edema of the face and extremities), polyadenopathies;

AND

3. Onset of symptoms 2 to 21 days after vaccination;

AND

4. Duration of event ≥ 3 days.

Any suspected clinical case of CHIKV-associated event shall be referred to a clinical expert, be evaluated according to standard diagnostic procedures and treated according to current medical standard until resolved or stabilized.

All AESI will be identified by Investigator assessment, using the symptoms listed above as a guideline, and will be recorded on the CRF. AESI are only captured from 2 to 21 days post-vaccination. Only those AEs identified as AESIs on the CRF will be included in the analysis of AESIs.

All AESIs will be adjudicated by the DSMB to see if the board agree with the investigator decision. Adjudication will be a Y/N flag from the DSMB for each AESI case. This will be added into the database and used for additional reporting.

Additionally, subjects presenting with acute arthralgia within 2 to 21 days post-vaccination will be followed-up until resolution and monitored for recurrences until the end of the study.

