12.4 Randomization and Blinding

The approximately 402 subjects will be block-randomized into the three study arms in a ratio of 1:1:1 at Visit 1 as described in Section 12.1.

In order to minimize/avoid bias, assignment into one of these study arms will be blinded for these subjects and the site staff, as well as the biostatistician (i.e. double-blind).

Each subject will have a unique subject identification code obtained from the interactive voice response system/interactive web response system (IXRS) assigned at the screening visit. The Investigator will keep a record (i.e. the subject screening log) of subjects who entered screening.

Randomization will be performed via the IXRS. At Day 1 (Visit 1, day of vaccination) eligible subjects will be assigned to the respective IMP Lot.

An overview of persons who will be (un)blinded is provided below:

Unblinded:

- DSMB voting members;
- Bio-statistician preparing unblinded analysis for the DSMB.

Blinded:

- Investigators and all other study staff involved in study conduct, safety assessments and IMP handling (i.e. perform preparation of the study vaccine, maintain the drug accountability logs detailing the dates and quantities of IMP administered to each subject);
- Study participant;
- Bio-statistician (except the one involved in DSMB);
- CRA's responsible for monitoring study data, IMP handling and verifying drug accountability (during the study and performing overall drug accountability);

- All laboratory personnel at central laboratories for safety and immunogenicity laboratory assessments;
- All other Sponsor and CRO staff including medical monitor and laboratory personnel at the Sponsor's labs for additional testing procedures.

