17.9 Adverse Events of Special Interest (AESI)

In addition to nonspecific transient muscle pain and joint pain that may occur after vaccination with any vaccine, subjects will be carefully monitored for signs and symptoms suggesting an acute stage CHIKV-associated event.

If a subject develops symptoms suggestive of CHIKV infection, he/she will be asked to contact the site immediately for clinical evaluation at an unscheduled visit.

Therefore, the following cluster of symptoms with or without remissions or exacerbations will receive particular consideration:

1. Fever ($\geq 38.0^{\circ}\text{C} / 100.4^{\circ}\text{F}$ measured orally);

AND

2. Acute (poly)arthralgia/arthritis most frequently in the extremities (wrists, ankles and phalanges, often symmetric), back pain and/or neurological symptoms (e.g. confusion, optic neuritis, retinitis/uveitis meningoencephalitis or polyneuropathy) and/or cardiac symptoms (e.g. myocarditis);

OR

One or more of the following signs and symptoms: macular to maculopapular rash (sometimes with cutaneous pruritus (foot arch) and edema of the face and extremities), polyadenopathies;

AND

3. Onset of symptoms 2 to 21 days after vaccination;

AND

4. Duration of event ≥ 3 days.

Any suspected clinical case of CHIKV-associated event shall be referred to a clinical expert, be evaluated according to standard diagnostic procedures and treated according to current medical standard until resolved or stabilized. For more detailed information please refer to: French guidelines for the management of chikungunya - acute and persistent presentations (Simon, Javelle et al. 2015).

Additionally, subjects presenting with acute arthralgia within 2 to 21 days post-vaccination will be followed-up until resolution and monitored for recurrences until the end of the study.

A blood sample for laboratory investigation will be taken upon presentation of the subject. Testing may include but is not limited to rheumatoid factor (RF), anticitrullinated protein antibody (ACPA), Ferritin and CRP. Retrospective investigation of a pre-vaccination sample may be considered for a thorough causality assessment.

Suspected CHIKV-associated events do not constitute a reason for withdrawal from the study.

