17.10.2 Adverse Events of Special Interest (AESI)

Any AESI should be reported to the Safety Desk by fax or email within 48 hours after the Investigator has become aware of the event. Under certain circumstances the initial notification could be done by phone, but nevertheless a written AESI Report Form has to be submitted to the Safety Desk within 48 hours (see Section 4).

Subjects will be carefully monitored for development of AESIs. A cluster of symptoms (see 17.9) associated with CHIKV infection, are defined as AESI. In case an AESI is identified, the Investigator will complete the AESI Report Form with all available information including medical records. This information will be provided to the DSMB. The DSMB will perform a thorough review of each case and advise whether additional clinical work-up is required.

The DSMB will conduct a final adjudication of all AESIs and will assess whether cases were new in onset and whether there is any relationship to administration of the study vaccine. Narratives with detailed case descriptions will be provided for all AESIs.

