6.1 Changes from Protocol

The Per Protocol analysis set uses different visit windows to define out of window results than outlined in the protocol schedule of events. This is in order to align the visit windows allowable in this analysis in line with the phase 1 study of this vaccine. The visit windows in the protocol are shown in section 11.2, whilst the windows for the exclusion from the Per Protocol analysis set are outlined in Section 9.5.2. Further, if an Unscheduled Visit falls into a Scheduled Visit window that either did not occur or occurred outside of the defined Scheduled Visit window, the Unscheduled Visit will be used in analyses in the place of the Scheduled Visit.

The definition of adverse event of special interest in section 11.7.5 has been updated per FDA feedback for clarification of the anatomical location with cutaneous pruritus. This is not yet reflected in Protocol version 3.0, which is the approved version at the time of SAP finalization.

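### AESI counts rest on investigator flags alone: DSMB adjudication covers only flagged cases, and no systematic search for unflagged symptom clusters is described

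*SAP*

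**What the plan says.** **Who flags.** SAP 11.7.5: "All AESI will be identified by Investigator assessment, using the symptoms listed above as a guideline, and will be recorded on the CRF". The next rule closes the set: "Only those AEs identified as AESIs on the CRF will be included in the analysis of AESIs". Protocol 12.4 lists investigators as blinded.

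**Who adjudicates.** SAP 11.7.5: "All AESIs will be adjudicated by the DSMB to see if the board agree with the investigator decision". The form is stated too: "Adjudication will be a Y/N flag from the DSMB for each AESI case". The SAP describes the result as additional reporting. Protocol 17.10.2 gives the board a wider remit: "The DSMB will conduct a final adjudication of all AESIs and will assess whether cases were new in onset", together with relationship to the vaccine. The AESI Report Form that goes to the board is completed once an AESI has been identified.

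**Blinding of the adjudicators.** Protocol 12.4 lists "DSMB voting members" as unblinded.

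**How it is reported.** The summary table in SAP 13.5.1 shows investigator-assessed and DSMB-assessed AESIs as separate lines, with Fisher's exact test across the three lots.

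**The symptom list.** Protocol 17.9 gives as neurological examples "confusion, optic neuritis, retinitis/uveitis meningoencephalitis or polyneuropathy". The list in SAP 11.7.5 lacks retinitis/uveitis. For the AESI definition, SAP 6.1 declares one update only, made "for clarification of the anatomical location with cutaneous pruritus".

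**The concern.** The AESI is a combination of findings: fever of at least 38.0 °C, a qualifying sign, onset 2 to 21 days after vaccination, and duration of at least 3 days. Under protocol 17.2.1 each symptom is normally its own AE, and fever, joint pain and rash are separate solicited terms in the eDiary (protocol 17.3). A subject can therefore meet the definition across several AE rows without any row carrying the AESI flag. Such a subject is absent from every AESI table. The separate tables of fever, arthralgia and rash do not fill the gap, because they do not show which findings occurred together in one subject.

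All three arms receive the same live-attenuated vaccine. With no control arm, the absolute AESI rate is the main information this trial gives on a chikungunya-like syndrome, and missed cases lower it directly.

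**Working it through.** The plan states no AESI rate, AESI power or adjudication-agreement figure, so there is nothing to reproduce. The check is mainly one of logic; the numbers are illustrations on assumed inputs.

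**Step 1: direction.** Let I be the set of CRF-flagged cases and D the set the DSMB confirms. D is formed by a yes/no on each member of I, so D is contained in I. Hence the DSMB count is at most the investigator count, with equality only if the board agrees with every case. A true case outside I is outside D as well.

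**Step 2: expected counts.** N = 402 is the planned sample size (protocol 18.1). The true rate p, investigator sensitivity se and specificity sp are assumed. Then:

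- true cases = N·p
- flagged = N·p·se + N·(1−p)·(1−sp)
- missed = N·p·(1−se)
- DSMB count = a·(true flags) + b·(false flags), with a and b between 0 and 1

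For p = 1%, se = 70%, sp = 99.5%: true flags 402 × 0.01 × 0.70 = 2.81; false flags 402 × 0.99 × 0.005 = 1.99; flagged 4.80; missed 402 × 0.01 × 0.30 = 1.21.

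| p | se | sp | True | Flagged | Missed | DSMB count (a = 1, b = 0) |
|---|---|---|---|---|---|---|
| 0.5% | 70% | 100% | 2.0 | 1.4 | 0.6 | 1.4 |
| 1% | 90% | 100% | 4.0 | 3.6 | 0.4 | 3.6 |
| 1% | 70% | 100% | 4.0 | 2.8 | 1.2 | 2.8 |
| 1% | 70% | 99.5% | 4.0 | 4.8 | 1.2 | 2.8 |
| 3% | 70% | 100% | 12.1 | 8.4 | 3.6 | 8.4 |

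In the third row, if the board agrees with only 80% of true cases, its count is 0.8 × 2.81 = 2.25. Over the range p = 0.5% to 3% and se = 70% to 100%, missed cases run from 0 to 3.6, and adjudication recovers none. The fourth row shows that over-flagging can put the investigator count above the true number.

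**Step 3: what zero flags would mean.** If none of 402 vaccinated subjects is flagged, the upper limit of the exact two-sided 95% interval is 1 − 0.025^(1/402) = 0.91%. With no false flags this limit applies to p·se, so the limit for p is 0.91%/se. At se = 90% it is 1.0%; at se = 50% it is 1.8%. The 50% to 90% range is a pure assumption with no basis in the documents.

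**Step 4: can a program screen for the cluster?** Only for candidates. Onset days 2 to 21 are 20 days. The eDiary covers the first 10 days after vaccination, so it reaches days 2 to 10, or 9 of the 20. For the other 11, daily temperature is not required (protocol 17.2.2.3), and a screen must rely on AE entries. Neurological signs, cardiac signs and polyadenopathy are not solicited at any time. AE start and stop dates are recorded throughout (protocol 17.2.1).

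**Step 5: timing.** With vaccination as Day 1, the last qualifying onset is Day 22, and three days counted inclusively end on Day 24. The earliest in-window Visit 3 is Day 25 (29 − 4). The screen can therefore be run before the Part A unblinding.

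**The case against.** The case against is substantial, and much of it stands.

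- A reader might infer that the DSMB sees only flagged cases. Protocol 17.11.1 contradicts that: the board also reviews listings and tables of solicited and unsolicited AEs. Only the formal yes/no is limited to flagged cases.
- A reader might infer that a missed case can never surface. The board can suggest an unscheduled visit; the sponsor reviews blinded safety listings until the last subject reaches Day 29 (protocol 17.11.2); investigators go through the questionnaires with each subject; and subjects with suggestive symptoms are told to contact the site. These are real safeguards, but none is written as a check for unflagged AESIs.
- A reader might infer that the AESI rate is biased downward overall. That is not shown. Removing false positives is a proper purpose of adjudication, and the net error depends on unknown sensitivity and specificity. Any loss comes from relying on the investigator flag alone, not from adjudication.
- A reader might infer that the lot comparison of AESIs is unblinded. The main analysis uses flags from blinded investigators, and both versions are tabulated. The documents do not say whether lot appears in the adjudication files, and the DSMB charter, which may settle it, is not among them.
- A reader might apply the Phase 1 medium-dose fever rate to 402 subjects to size the pool of cases. That rate comes from a group of 30 given a liquid formulation at a different dose level, and fever alone does not meet the cluster.
- The missing retinitis/uveitis sits in a list of examples, so the definition is not clearly narrowed.

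**Conclusion.** The point holds in a limited form. The AESI analysis counts only what blinded investigators flag, the DSMB flag covers only those cases, and no systematic search for unflagged clusters is described. That the DSMB-assessed rate cannot exceed the investigator-assessed rate follows from the text without any assumption. How many cases would be lost is unknown: 0 to 3.6 of 402 over the assumed grid. The listing reviews reduce the risk but do not guarantee that a missed cluster is found.

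The adjudicators' unblinded status is a secondary matter. It touches only the DSMB-assessed comparison between lots, and only if lot is visible at adjudication. The difference between the two symptom lists is genuine and undeclared, but minor. The primary immunogenicity analysis is not affected. This is a cheap improvement to a key safety rate, not a flaw that undermines the trial.

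**What to change.** 1. In SAP 11.7.5, add a blinded programmed screen of AE and eDiary records for candidate clusters: fever plus a qualifying sign, onset 2 to 21 days after vaccination, duration of at least 3 days. State that it relies on AE entries after the eDiary period and that it finds candidates, not confirmed cases.
2. Run it before unblinding for Part A, and send every unflagged match for adjudication with lot masked. State the masking in the SAP and the DSMB charter.
3. Report programmed-candidate, investigator and DSMB counts side by side as a sensitivity analysis, and keep the investigator-flag analysis as main. SAP 11.7.6 already does something similar with its recall flag for solicited AEs.
4. Reconcile the symptom lists in protocol 17.9 and SAP 11.7.5, and declare in SAP 6.1 any difference that remains.

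The cost is one program and some wording in the SAP and charter. The downside is that the DSMB reads some additional cases that turn out negative.
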